Statistical Analysis Plan

A Trial of Online LGBTQ-affirmative Cognitive Behavioral Therapy to Reduce Depression and Associated Health Risks Among Young Adults
NCT04408469

01/18/2023

Intervention efficacy will be assessed using an intent-to-treat analysis and include all participants (n = 120). First, dependent variables and stigma moderators will be assessed for normality using skewness thresholds of ≥ 2 and kurtosis thresholds of ≥ 7 . If scales violate assumptions of normality, they will be square root transformed.

To examine the efficacy of LGBTQ-affirmative ICBT, we will use linear mixed models with maximum likelihood estimation and an unstructured covariance matrix to test the Condition × Time interaction effects between conditions over time for all continuous mental health outcomes (BSI, CESD, ODSIS, OASIS). For binary outcomes (suicidal thoughts, problematic drinking, SIDAS, sex-risk behavior), we will test intervention efficacy using a generalized linear mixed model with a logit link and a binomial distribution to test the Condition × Time effect predicting odds of each binary outcome between conditions over time. Primary efficacy analyses between conditions will include baseline (time = 0), immediate post-intervention (time =1), and 4-month follow-up (time = 2) to model the Condition × Time effect of receiving LGBTQ-affirmative ICBT (condition = 1) versus self-monitoring (condition = 0). Effect sizes (Cohen's d) for linear mixed models will be calculated as mean pre-post change (e.g., pre-intervention to post-intervention, pre-intervention to 4-month follow-up) in the LGBTQ-affirmative ICBT intervention minus the pre-post change in the self-monitoring condition, divided by the pooled baseline standard deviation.

To examine whether Condition × Time effects varied as a function of baseline levels of heterosexist stigma (i.e., internalized stigma, interpersonal stigma, and structural stigma), we will conduct moderation analyses using linear mixed models with maximum likelihood estimation, unstructured covariance matrix, and three-way interactions of Condition × Time × Stigma.

Moderation by internalized, interpersonal, and structural stigma will be entered together into

multivariable models for each outcome. Significant three-way interactions of Condition \times Time \times Stigma will be further probed and plotted to contrast high stigma (one standard deviation above the mean) with low stigma (one standard deviation below the mean). All results will be evaluated at p < .05.

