or tablet device; (5) ability to read, write, and speak in English; and (6) provision of informed consent.

Exclusion criteria. Participants will be excluded for any of the following: 1) current active suicidality or homicidality (defined as active intent or concrete plan, as opposed to passive suicidal ideation); 2) evidence of active mania, psychosis, or gross cognitive impairment that could interfere with the participant's ability to volitionally consent to research or interfere with their ability to safely and reliably complete research; 3) current enrollment in an intervention study; 4) current enrollment in intensive mental health treatment (i.e., receiving mental health treatment more than once per month or 8 or more sessions of CBT within the past year.

5. **Describe** how access to the population will be gained in the study.

We will advertise for our study online, via our past study participants who expressed interest in knowing about future studies, via advertisements sent to local LGBTQ-serving organizations, and through study participants' word of mouth. Advertisements will engage treatment-seeking LGBTQ by emphasizing the study as a safe venue for addressing mental health and associated risks.

6. **Participant classification:** Check off all classifications of participants that will be specifically recruited for enrollment in the research project. Will participants who may require additional safeguards or other considerations be enrolled in the study? If so, identify the population of participants requiring special safeguards and provide a justification for their involvement.

Children	🔀 Healthy	Non-English Speaking	Prisoners
Economically disadvant	aged		
Decisionally Impaired	Employees	Pregnant women	
Yale Students			
Other vulnerable popula	tion (who?):		
Psychology Pool			

NOTE: Is this research proposal designed to enroll children who are wards of the state as potential participants? \Box Yes \boxtimes No (If yes, see HRPP Policy 310.4 for further requirements)

7. **Inclusion/Exclusion Criteria:** What are the criteria used to determine participant inclusion or exclusion?

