4) Peer-recruitment and referrals by previous and current study participants. Participants in the study will be asked to distribute study recruitment materials to peers who may be interested in participating in the study. Participants will be reminded that staff will never disclose any information about an individual's participation in the study, but that participants are free to disclose information about their own participation to whomever they desire. Participants are not required to distribute recruitment materials as a condition of study participation and the strictly voluntary nature of this request will be emphasized by study staff.

Recruitment text and images are attached to this application.

Are you collecting any information about the individuals prior to their signing a consent form? Yes \square No \boxtimes

If yes, indicate what information you will be collecting and how it will be gathered *(phone screen, paper questionnaire, etc.)*

2. **Indicate recruitment methods below.** Attach copies of any recruitment materials that will be used.

\boxtimes	Flyers	🛛 In	ternet/Web Postings	Radio
	Posters	$\boxtimes M$	ass E-mail Solicitation	🛛 Telephone
_	Letter		epartmental/Center Website	Television
imes	Newspaper			
\boxtimes	Through local NGO or other local conta	act	Social Media (Facebook, Twitter	ſ)
	Classroom recruitment			
	Table set-up / in-person recruitment of	public		
imes	Snowball sampling			
	Other (describe):			

3. Targeted Enrollment: Give the number of participants:

- a. Targeted for enrollment for this protocol: 120 (plus an additional 14 participants who will pilot the study)
- b. If this is a multi-site study, give the total number of participants targeted across all sites: N/A

4. How was this estimate derived?

We aim to recruit 120 participants into this study. Our primary aim is to demonstrate a greater reduction in 4-month follow-up in depressive symptoms in the online EQuiP condition compared to the self-monitoring control. Using a 1:1 randomization, we will randomly assign 60 participants to each of the two conditions (i.e., online EQuIP and the self-monitoring control). Assigning 60 participants into each condition will allow us to detect a difference ($\beta = 0.2, p < .05$) consistent with the average effect of online CBT involving therapist support (compared to a weak control condition) found across meta-analyses of online CBT: .61 (Andersson & Cuijpers, 2009), .83

Page 8 of 22

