member with a trusted social network member for the clinical team member to counsel about next steps. In the event that the participant cannot identify or connect the clinical team member with an available person in their support network (such as a family member, partner, or friend), the clinical team member will contact 911 to dispatch local paramedics. Only the minimal necessary identifying information will be provided to these personnel. In less imminent instances of distress, we will refer distressed participants to local mental or behavioral health services available in their area. All therapy homework will be reviewed by a clinical staff member trained in suicide assessment. Research and clinical staff members will receive an alert if the participant answers the online questionnaires in a manner that signals distress; such participants will be called by a clinical staff member to assess risk. A clinical team member will also be on-call during phone screeners and will be asked to speak with any participant who reports imminent distress to the research team member conducting the phone screener. The protocol also outlines a step by step procedure for reporting suspected child abuse.

Participants will be notified of the reporting requirements under these circumstances during the consent process.

- 10. **Consent/Consent Waiver: In certain circumstances, the IRB may grant a waiver of documentation of consent, or a full waiver of consent, depending on the study.** If you will request either a waiver of consent, or a waiver of signed consent for this study, complete the appropriate section below.
 - I plan to obtain signed consent
 - I plan to obtain verbal or online consent

I plan to obtain signed consent for part of the study, and verbal or online consent for another part of the study.

I do not plan on obtaining consent due to the nature of the study (explain):

Requesting a waiver of documentation of consent (Note that an information sheet may be required.)

If requesting a waiver of documentation of consent, please address the following: a. Would the signed consent form be the only record linking the participant and the research? \Box Yes \Box No

b. Does a breach of confidentiality constitute the principal risk to participants? Yes No

OR

a. Does the research pose greater than minimal risk? Yes *If you answered yes, stop. A waiver cannot be granted.* No

AND

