The full packet of study measures and assessments is attached to this application. We propose to collect information about participants' general mental health status, including demographics; depressive and anxious symptoms and suicidality; substance use; sexual-risk behavior; HIV status; experiences with stigma-related stress; cognitive, affective, and interpersonal functioning (e.g., rumination, social support, impulsivity, assertiveness); mental health treatment history and perspectives; and perceptions of intervention helpfulness. For participants in the active treatment conditions (online EQuIP), we will also collect participants' homework assignment text regarding the above topics and therapists' homework feedback. Therapists will document all phone contact on a password-protected file stored on Yale's HIPAA-compliant Secure Box.

Participants will provide the following data at baseline, 4-month (immediate post-treatment) followup, and 8-month follow-up appointments: quantitative assessments, previously used with LGBTQ young adults, of mental health, suicidality, substance use, sexual-risk behavior, and stigma-related stress, and (at 4- and 8-month follow-ups only) intervention acceptability.

Page 12 of 22

The 20 participants from the Online EQuIP condition will provide feedback in regard to their experience in completing the treatment (e.g., things they liked, things they did not like, things they would change). Pending consent from participants, these interview will be audiorecorded.

The 14 participants who will take part in the initial pilot trial will complete baseline and immediate post-treatment (3-month followup) assessments as well as a qualitative interview about their experience at 3-month followup. These participants will not complete the 6-month followup assessment.

2. Will any of the following identifiers be collected?

Names 🛛

All geographic subdivisions smaller than a State, including: street address, city, county, precinct, zip codes

 \boxtimes Telephone numbers

Fax numbers

 \boxtimes E-mail addresses

Social Security numbers

Medical record numbers

Health plan beneficiary numbers

Account numbers

 \square All elements of dates (except year) for dates related to an individual, including: birth date, admission date, discharge date, date of death, all ages over 89 and all elements of dates (including year) indicative of such age, except that such ages and elements may be aggregated into a single category of age 90 or older

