After study completion, data will be stored on an encrypted, password-protected server at the Yale School of Public Health. The identifiable data will remain separate from the remainder of participant data. After three years of study completion, the link to personal identifiers will be destroyed.

Deidentified audio recordings, labeled only with study IDs, will be transcribed using GoTranscript, a confidential external transcription service. GoTranscript protects audio files with 2048-bit SSL encryption. Audio files for transcription are cut into 5-10 minute chunks and transcribed by different transcriptionists who have each signed non-disclosure agreements. Audio files are deleted from GoTranscript servers upon transcript completion and will then be uploaded by study staff to

Yale's Secure Box folder. After three years from study completion, audio transcripts will be destroyed.

8. Will a Certificate of Confidentiality be needed? (*See also the NIH Certificate of Confidentiality Kiosk, http://grants.nih.gov/grants/policy/coc/index.htm*)

We will request an NIH Certificate of Confidentiality for the full randomized control trial.

SECTION VII: POTENTIAL RISKS AND BENEFITS

9. **Risks:** Describe the reasonably foreseeable risks, including risks to participant privacy, discomforts, or inconveniences associated with participants participating in the research. *Note: All studies have the potential for risk, if not physical, there may be psychological, reputational, or financial risks or risks to breach of confidentiality*

Study participants are at minimal risk for harm as a result of participation in the proposed research study. Although unlikely, one risk of the proposed study is that participants will experience emotional discomfort as a result of completing the quantitative assessments, intervention, and phone interviews. Breach of participants' confidentiality presents another possible risk. The investigative team's strategies to protect against both risks are described below.

10. Minimizing Risks: Describe the manner in which the above-mentioned risks will be minimized.

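### The SAP plans no by-arm summary of adverse events, new-onset suicidal thoughts or individual deterioration, so new cases offset by resolved ones would appear in no planned trial result

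*SAP*

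**What the plan says.** **Named risk.** Protocol Section VII, item 9 (Risks) states that "one risk of the proposed study is that participants will experience emotional discomfort as a result of completing the quantitative assessments, intervention, and phone interviews". It calls this unlikely and rates overall risk as minimal.

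**Data collected.** Suicidality and symptoms are surveyed in both arms at baseline, month 4 and month 8 (Research Plan; Section VI, item 1). Staff "will receive an alert if the participant answers the online questionnaires in a manner that signals distress", and a clinical staff member then calls the participant (Section V, item 9). "Therapists will document all phone contact on a password-protected file" (Section VI, item 1).

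**Entry.** The exclusion criteria cover "current active suicidality or homicidality (defined as active intent or concrete plan, as opposed to passive suicidal ideation"). Participants with passive ideation can therefore enroll, and the sample can hold both baseline-positives and baseline-negatives for suicidal thoughts.

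**Monitoring.** The Data and Safety Monitoring Plan (Section VII) has the principal investigator review safety quarterly. Reportable events go to the IRB in writing, and the monitoring board hears of serious or unanticipated adverse events within 5 days. The form's template asks for attribution and grading of adverse events; the text supplied gives no grading scheme and no by-arm tabulation.

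**Analysis.** The SAP has linear mixed models for BSI, CESD, ODSIS and OASIS, logistic mixed models for suicidal thoughts, SIDAS, drinking and sexual risk, an effect-size formula, and stigma moderation. The binary models serve "to test the Condition × Time effect predicting odds of each binary outcome between conditions over time". The closing rule is "All results will be evaluated at p < .05". No harms output is described.

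**The concern.** A Condition × Time odds effect answers whether the proportion with suicidal thoughts shifted differently in the two arms. It does not say how many participants developed such thoughts, because each new case is set against a resolved one. Mean symptom change likewise does not count those who got worse.

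The trial tests a remotely delivered therapy, adapted from a protocol that uses emotional exposure, in people aged 16 to 25 selected for depression or anxiety symptoms. Readers of the results will ask whether some participants were made worse. The survey data to address this will exist in both arms, but a team following the SAP as written would produce no table that does so.

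**Working it through.** **1. What the two documents would produce, by arm**

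| Question | Planned by-arm result? |
|---|---|
| Average symptom worsening | Yes: linear mixed models |
| Net change in suicidal thoughts or SIDAS | Yes: logistic mixed models |
| New-onset suicidal thoughts among baseline-negatives | No |
| Number deteriorating on each symptom scale | No |
| Adverse events, alerts, clinical-protocol activations | No: individual handling and reporting only |

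**2. The plan's own figure.** The sample size rests on the smallest of three standardised effects, "found across meta-analyses of online CBT: .61", with 80% power and alpha 0.05 (two-sided assumed).
- n per arm = 2 × (1.96 + 0.842)² / 0.61² = 15.70 / 0.3721 = 42.2, so 43.
- Allowing for 25% attrition: 43 / 0.75 = 57.3, so 58. The planned 60 is reproduced to within 2.
- Expected to be assessed: 60 × 0.75 = 45 per arm.

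This sizing is for efficacy; no figure is given for any harm.

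**3. Can new cases be hidden?** Positives at follow-up = baseline positives − resolved + new. The documents give no baseline rate, so 20%, 35% and 50% were assumed. A random-intercept logistic model was fitted by maximum likelihood to constructed tables with 60 per arm, using baseline and one follow-up (the SAP uses two follow-ups). P-values are from likelihood-ratio tests of the interaction.

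| Baseline positive, each arm | EQuIP resolved / new → follow-up | Control resolved / new → follow-up | Interaction OR (p) | New onset, EQuIP vs control |
|---|---|---|---|---|
| 12 (20%) | 6 / 6 → 12 | 2 / 2 → 12 | 1.00 (1.00) | 6/48 vs 2/48 |
| 21 (35%) | 10 / 10 → 21 | 2 / 2 → 21 | 1.00 (1.00) | 10/39 vs 2/39 |
| 12 (20%) | 11 / 4 → 5 | 2 / 2 → 12 | 0.20 (0.095) | 4/48 vs 2/48 |
| 21 (35%) | 18 / 5 → 8 | 3 / 2 → 20 | 0.14 (0.019) | 5/39 vs 2/39 |
| 30 (50%) | 24 / 6 → 12 | 4 / 2 → 28 | 0.14 (0.007) | 6/30 vs 2/30 |

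In the second row new onset is 25.6% against 5.1%. The difference is 20.5 points, with standard error √(0.256 × 0.744/39 + 0.051 × 0.949/39) = 0.078 and a Wald 95% interval of about 5 to 36 points (Fisher p = 0.025). The planned model reports no effect there. In the last two rows it reports significant benefit while EQuIP has numerically more new cases; those excesses are within chance (Fisher p = 0.43 and 0.25). At 20% baseline the benefit was not significant.

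**4. Precision of a harms table**
- Zero events: exact upper limit = 1 − 0.025^(1/n). This gives 7.9% at n = 45 and 6.0% at n = 60.
- New-onset denominators are smaller. With 16 of 45 positive at baseline, n = 29 and the limit is 1 − 0.025^(1/29) = 11.9%.
- Power to show a rise in worsening from 5% to 15% is 45% at 60 per arm and 35% at 45. From 10% to 20% it is 33% and 26%.

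**The case against.** The strongest reply is that harm is already visible where it matters. This largely stands against stronger readings.

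- A reader might infer that harm is never compared by arm. It is, on average: mean symptoms and net suicidality are compared at both follow-ups, and an adverse Condition × Time effect would show.
- A reader might infer that new and resolved cases always cancel. Cancellation is complete only when they balance; otherwise the model estimates the net shift, and net harm remains detectable.
- A reader might infer that participants who worsen go unreported. Serious or unanticipated events do reach the IRB and the monitoring board. What is missing is a planned by-arm result, and ordinary worsening or new passive ideation need not meet the reporting criteria.
- A reader might take the 0.61 SD effect and argue that many EQuIP participants must still deteriorate unseen. Treat 0.61 as change from baseline, with normal change of SD √(2(1 − ρ)). Worsening by at least 0.5 SD is then expected in about 3, 6 or 8 of 45 at ρ = 0.7, 0.5 or 0.3. A control arm with zero mean change gives about 12, 14 or 15. That comparison favours EQuIP and merely restates the mean effect. Deterioration counts add information only if the arms differ in the spread or shape of change.
- A reader might infer that the protocol expects EQuIP to trigger suicidal thoughts. It names emotional discomfort only, and surveys at months 4 and 8 would miss brief discomfort during sessions.

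Two practical objections also stand. The SAP is dated 01/18/2023, after the follow-up that the protocol's payment section expected to end in February 2022, so thresholds added now cannot be called prespecified before data collection. And the protocol says alerts are sent, not that a log suitable for tabulation is kept.

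None of this supplies the missing table.

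**Conclusion.** The gap is real and should be closed. Neither document plans a by-arm count of adverse events, new-onset suicidal thoughts or individual deterioration. The net odds model can be null, or favourable, while new onset differs between arms: 10/39 against 2/39 with an odds ratio of 1.00 in the worked case.

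That size rests on assumed baseline rates and assumed numbers of new and resolved cases, in a two-occasion version of the model. It shows what the planned output cannot distinguish and is no evidence that EQuIP does harm. The efficacy estimates are unaffected. What changes is whether the report can say anything about who got worse, and at 45 to 60 per arm that statement will be descriptive.

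**What to change.** Add one harms paragraph and one table to the SAP.

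1. **From the surveys common to both arms, at month 4 and month 8**, give by arm the number, denominator, risk difference and 95% confidence interval for:
   - new-onset suicidal thoughts among those without them at baseline;
   - new positives on the SAP's binary SIDAS outcome among baseline-negatives;
   - deterioration on BSI, CESD, ODSIS and OASIS, against a stated threshold chosen without reference to arm-level results.
2. **Missing follow-up.** Report the number missing by arm and a simple sensitivity analysis, for example counting all missing as worsened and then none. Participants who worsen may be those who leave, and 25% attrition is planned.
3. **Events.** Tabulate by arm serious or unanticipated adverse events and, where records exist, clinical-protocol activations and alerts. Note that detection during treatment differs: controls complete a weekly online survey, while EQuIP participants have homework reviewed by clinical staff.
4. **Labelling.** Call the table descriptive and imprecise, exempt it from the SAP's blanket significance rule, and do not present its thresholds as set before data collection.

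The cost is one paragraph, one table and some retrieval of event records. No new visits, participants or survey data are needed, and no efficacy analysis changes.

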(Sztein, Koransky, Fegan, & Himelhoch, 2018), and 1.00 (Spek, Cuijpers, et al., 2007). This estimate accounts for 25% attrition at 3-month follow-up, consistent with the attrition rate in our current in-person treatment study of 254 young gay and bisexual men and exceeding that found in our previous online intervention research (e.g., [name] & Goldfried, 2010).

Before we randomize participants into the full trial, we will pilot-test the online EQuIP treatment with 14 LGBTQ young adults who meet all eligibility criteria employed for the full trial. The purpose of this initial test is to ensure acceptability of the treatment content and usability of the technical platform.

5. **Process of Consent/Assent** (*NOTE: When a study includes minors, parent provide permission [not consent] for the child's participation, and the child provides assent for participation)*

Describe the setting and conditions under which consent/assent will be obtained, including parental permission or surrogate permission and the steps taken to ensure participants' independent decision-making.

Informed consent will be obtained for all participants at three points – before completion of the online screener, phone screener, and baseline survey.

Before completing the online screener, participants will review an online consent form describing the screening purpose and risks/benefits and indicate their consent by selecting the commensurate button. Participants' identifying information, including their name, will be kept in a separate database from the remainder of their study responses. Participants who are deemed preliminarily eligible based on the online screener will be contacted by our study staff to confirm eligibility by phone screen.

Before administering the phone screener, a project staff member will first assess participants' willingness and capacity to consent to completing the screener to determine eligibility. Participants will provide their verbal consent for the phone screener. Participants' identifying information, including their name, will be kept in a separate database from the remainder of their study responses.

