For the 14-person pilot study and larger RCT, the phone screener will be completed using Yale's secure Qualtrics server. Participants who are deemed eligible based on the phone screener will then be e-mailed a PDF copy of the consent form by the research assistant conducting the phone screen. The research assistant and participant will schedule a time to review the consent form via telephone, including details of the full study and study risks and precautions against risk, and address any points of confusion. The participant will then be given the opportunuity to provide verbal consent. Participants will then be given a username and password to log in to the secure online platform and asked to confirm that they were able to successfully access this platform. Upon receipt of this confirmation, participants will be sent their baseline surveys. Thereafter, study participation begins when the participant completes their baseline surveys. After completion of these surveys, participants will be randomized to one of two conditions.

6. Evaluation of Participant(s) Capacity to Provide Informed Consent/Assent: Indicate how the personnel obtaining consent will assess the potential participant's ability and capacity to consent to the research being proposed, if applicable

Prior to sending the link for the baseline survey, a trained research assistant will assess participants' consent by phone. The RA will ensure that the participant understands the risks associated with the disclosure of information that could indicate imminent threat to self or others. Verification of comprehension of informed consent will be accomplished by asking participants to recall central points in the consent process; points of confusion will be clarified. Once participants have fully understood the consent, they will be asked to provide verbal consent. RAs will be instructed to contact the PI or project coordinator if he or she is unsure about any participant's capacity to consent.

For the phone screener, participants will be asked to provide verbal consent prior to answering the screener questions.

7. **Documentation of Consent/Assent:** Specify the documents or verbal scripts that will be used during the consent/assent process. Copies of all documents should be appended to the protocol, in the same format that they will be given or spoken to participants.

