All participants and potential participants will be provided with a list of community referrals, including, as available in each participants' region, psychological, medical, HIV/STD testing, substance use, and housing supports. Notably, we intentionally recruit participants from low-resources regions as a matter of the capacity of our intervention to serve as a needed public health response.

2. **Payments for Participation (Economic Considerations):** Describe any payments that will be made to participants, if any, the amount and timing of payments and the conditions for receiving this compensation (if applicable). If you plan to hold a drawing, be sure to include the following on any consent or recruitment materials mentioning the sweepstakes: 1) the value of the prize; 2) the sponsor of the prize (this cannot be a federal funding source); 3) the odds of winning; 4) that there are no restrictions to winning.

Participants will receive \$30 for completing the baseline assessments, \$30 for completing the 3month follow-up assessments, \$10 for each weekly session or mood tracking survey completed, and \$30 for completing the 6-month follow-up assessment (total = \$190). Payment will be prorated for partial study completion (i.e., participants will only be paid for the parts of the study that they completed). Participants who participate in the phone interview will receive \$30. All study payments will be in the form of e-mailed Amazon gift cards or Venmo payments. Venmo payments will be sent to participants from the private @Yale-Study account and will be accompanied with the text "Thank you for your time."

Starting in September 2021, as participants start to become eligble to complete their final follow-up assessments, we will hold a monthly sweepstakes for all randomized participants who successfully completed their 8-month follow-up assessment in the past month. Each month, the sweepstakes winner will be selected using a random number generator. Winners will receive \$100 via Amazon gift cards or Venmo payments (as per their indicated preference) and will be notified via email directly after the selection of the sweepstakes winner. We will hold this monthly sweepstakes each month from September 2021 until February 2022, when the last randomized participant will have completed their final follow-up assessment.

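### The planned mixed model and change-based Cohen's d leave the baseline arm difference free although randomisation follows baseline; a common baseline mean would cut the variance by about 12–29% for the continuous outcomes

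*SAP*

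**What the plan says.** For the continuous outcomes (BSI, CESD, ODSIS, OASIS) the SAP specifies "linear mixed models with maximum likelihood estimation and an unstructured covariance matrix to test the Condition × Time interaction effects between conditions over time". Baseline is one of the modelled visits: "Primary efficacy analyses between conditions will include baseline (time = 0), immediate post-intervention (time =1), and 4-month follow-up (time = 2"). The population is all randomised participants: "intent-to-treat analysis and include all participants (n = 120"). The effect size is the pre-post change in the treatment arm "minus the pre-post change in the self-monitoring condition, divided by the pooled baseline standard deviation".

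The SAP does not list the fixed effects, does not say whether time is categorical or linear, and mentions neither a common baseline mean nor a baseline covariate.

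The protocol (Section V, item 5) fixes the order of events: "After completion of these surveys, participants will be randomized to one of two conditions". Its sample-size paragraph (Section V, item 4) plans 60 per arm for a difference in depressive symptoms at the 4-month assessment, citing effects of .61, .83 and 1.00, and adds: "This estimate accounts for 25% attrition at 3-month follow-up".

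**The concern.** A Condition × Time model with baseline at time 0 ordinarily contains a condition main effect, and that main effect is the baseline difference between arms. The definition of d points the same way, because each arm's own baseline is subtracted. Since allocation happens after the baseline surveys, any baseline difference is chance. Estimating it, then subtracting it in full from the follow-up difference, carries baseline sampling error into the treatment effect. A model that gives both arms one baseline mean targets the same quantity without that error.

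What is at stake is precision: wider intervals on all four continuous outcomes and lower power for the comparison on which the sample size rests. Bias is not at issue.

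**Working it through.** **Inputs.** From the protocol: 60 per arm, 1:1 allocation, power 80%, alpha .05 (two-sided assumed, as sidedness is not stated), smallest cited effect .61, attrition 25%, hence 60 × .75 = 45 follow-ups per arm. The protocol attaches the 25% to a 3-month visit but sets the aim at 4 months; I apply it to the post-treatment assessment. Assumed: pre-post correlation ρ from .3 to .7, and equal SDs at the two visits, set to 1.

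**The plan's own figure.** Comparing follow-up means and ignoring baseline, n = 2(1.96 + 0.84)²/.61² gives 43 per arm, or 43/.75 = 58 after attrition. The exact t calculation gives 44 and 59. The stated 60 reproduces. With 45 per arm the SE is √(2/45) = .211 and power at .61 is 82.5% (81.6% by t). The SAP tests a different contrast.

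**Variance of the contrast.** Under the planned model each arm's estimated change combines a residual part from the 45 followed participants with (ρ − 1) times the mean of all 60 baselines:

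- Planned: V = 2[(1 − ρ²)/45 + (1 − ρ)²/60]
- Common baseline mean: V = 2(1 − ρ²)/45
- Ratio, common to planned: 1/[1 + .75(1 − ρ)/(1 + ρ)]

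The second term of the planned variance is positive for every ρ below 1, so the planned contrast is always the less precise of the two.

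At ρ = .5: planned V = 2[.75/45 + .25/60] = .0417, SE .204. Common baseline V = 2 × .75/45 = .0333, SE .183. The ratio is .80, and 1/.80 = 1.25, so the gain is worth 25% more participants.

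Power is Φ(.61/SE − 1.96); the effect detectable with 80% power is 2.80 × SE.

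| ρ | Variance reduction | Power at .61, planned → common | Detectable effect, planned → common |
|---|---|---|---|
| .3 | 28.8% | 72.6% → 85.8% | .67 → .56 |
| .4 | 24.3% | 78.4% → 88.4% | .62 → .54 |
| .5 | 20.0% | 84.8% → 91.6% | .57 → .51 |
| .6 | 15.8% | 91.3% → 95.1% | .51 → .47 |
| .7 | 11.7% | 96.8% → 98.2% | .45 → .42 |

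**Two thresholds.**

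- Planned power at .61 equals 80% when SE = .61/2.80 = .218, which gives ρ = .425.
- The planned contrast is only as precise as ignoring baseline when (1 − ρ)²/60 = ρ²/45, that is (1 − ρ)/ρ = √(60/45) = 1.155, so ρ = .464. Below that value, subtracting baseline is worse than not using it.

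**Sensitivity.**

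- Complete data instead of 25% attrition: the ratio is (1 + ρ)/2, a reduction of 35, 25 and 15% at ρ = .3, .5, .7.
- Three visits, categorical time, equal correlations, generalised least squares: the same 28.8, 20.0 and 11.7% at both follow-ups.
- Linear time (0, 1, 2), equal correlations: the slope variance falls 33.6, 22.3 and 12.5%. The gain therefore does not depend on how time is coded.
- Correlation decaying with time (AR(1)): 38.5, 31.0 and 20.4% at the last visit.
- 35% attrition at the last visit, equal correlations: 26.1, 18.0 and 10.5% there.

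**Simulation.** Maximum likelihood with estimated unstructured covariance, 2,000 trials per cell, at ρ = .4, .5, .6: variance reductions of 23–26%, 19–21% and 14–16%; power at .61 of 79 → 89%, 85 → 91% and 91 → 94%. Mean estimates at ρ = .4 were .610 and .611. Type I error (z test) was 5.1–6.2% planned and 5.6–6.6% with a common baseline, with Monte Carlo SE about .5 points.

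**The case against.** The strongest reply is that nothing here is wrong. An unstructured mixed model with baseline as an occasion is a standard, unbiased analysis that already uses the baseline scores and keeps all 120 participants. Power falls below 80% only if ρ is under about .43 and the true effect is the smallest of the three cited. At .83, planned power is already about 94% at ρ = .3 and higher beyond that. All of this stands, and it limits the point to a loss of precision.

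The free baseline is inferred, since the SAP lists no fixed effects. That is true, but it is the ordinary reading, and if a constrained model was intended the text does not show it. The definition of d would also suit a common-baseline model if the changes were model-based; the SAP does not say whether they are.

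Changing the primary model late invites suspicion of a data-driven choice. The SAP is dated 01/18/2023, and the protocol (Section VIII, item 2) has the last sweepstakes running "from September 2021 until February 2022, when the last randomized participant will have completed their final follow-up assessment". This has force. Reporting the common-baseline model only as a sensitivity analysis protects the plan but leaves the primary interval and power as they are.

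The Condition × Time × Stigma models share the structure. No gain was calculated for them.

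**Conclusion.** The concern holds. As ordinarily read, the SAP spends information on a baseline difference that randomisation makes zero in expectation. At the protocol's 25% attrition, a common baseline mean reduces the variance of the treatment contrast by about 12% (ρ = .7) to 29% (ρ = .3), and keeps power at .61 above 80% across that range, where the planned contrast runs from 73 to 97%.

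The figures rest on an assumed ρ, equal variances, and attrition unrelated to outcome. They apply to BSI, CESD, ODSIS and OASIS and do not carry over to the logistic mixed models. The planned analysis is not invalid; this change should be made, but the trial's conclusions do not depend on it.

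**What to change.** For the four continuous outcomes, write the fixed effects into the SAP: categorical time, one baseline mean shared by both arms, and a Condition term at each follow-up visit, with unstructured covariance. Modelling the follow-up scores with the baseline score as covariate is an acceptable alternative. Compute Cohen's d from the model-based contrast at each follow-up, divided by the pooled baseline SD.

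Record with a date that the change preceded any examination of outcomes by arm. If that cannot be shown, keep the planned model as primary and report the common-baseline model as a labelled sensitivity analysis, accepting that the primary interval is then unchanged.

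The cost is a few lines of SAP text and one fewer parameter. No new data are needed, and under randomisation the estimand is the same.
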